9.5 Analysis Populations

The intent-to-treat (ITT) population will include all randomized subjects.

The full analysis set (FAS) or population is a subset of the ITT set from which subjects are excluded who did not receive any study drug or have a baseline aggregate five symptom score of ≤ 5 . For the secondary analyses of individual symptom scores and quality-of-life responses, further subjects who do not have a baseline score of >1 for that symptom or response will be excluded.

A PP population, defined as subjects who do not have a major protocol deviation prior to resolution of the aggregated five symptoms, will also be used as supportive evidence of efficacy. Subjects who are non-compliant with the requirements of the protocol after achieving resolution of the five COVID-19 symptoms will be included in the PP set due to the expectation that such subjects will likely discontinue prematurely from the study.

The safety population includes all subjects who received any amount of study treatment and will be the population for safety evaluations.

For each analysis population, baseline subject characteristics, including age, sex, race, ethnicity, height, weight, BMI and eGFR will be summarized by study arm (CTAP101 Capsules and placebo). Primary, secondary **methods** outcomes will be summarized by study arm and FU time points, using CONSORT guidelines to present descriptive statistics, including mean, median, standard deviation, quartiles, interquartile range, minimum, and maximum values for subjects within the site, overall and by treatment group. Continuous variables will be summarized using means, standard deviations, and quartiles, while categorical variables will be summarized using frequencies and percentages.

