4 ANALYSIS POPULATIONS

4.1 Intent-to-treat Population

The intent-to-treat (ITT) population will include all randomized subjects.

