4.3 Full Analysis Population

The full analysis set (FAS) or population is a subset of the ITT set from which subjects are excluded who did not receive any study drug or have a baseline aggregate five symptom score of >5. For the secondary analyses of individual symptom scores and quality-of-life responses, further subjects who do not have a baseline score of >1 for that symptom or response will be excluded.

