- 2. The number of days to resolution of the selected five COVID-19 symptoms (trouble breathing, chest congestion, dry or hacking cough, body aches and pains, and chills and shivering), defined as a reduction in the aggregate symptom score recorded on Day 0 (prior to study drug initiation) by the FLU-PRO Plus[©] questionnaire to or below 5 for a minimum of three consecutive days. These five symptoms are part of the chest/respiratory and body/systemic domains of the FLU-PRO Plus[©] questionnaire for which average scores of ≥1.5 were required for each domain for inclusion in the study. Trouble breathing, chest congestion and dry or hacking cough are symptoms indicative of potentially inadequate oxygenation and an impending requirement for supplemental oxygen and hospitalization. Body aches and pains and chills and shivering are symptoms indicative of systemic inflammatory responses associated with active viral infection. Resolution of each of these five symptoms will be analyzed separately, as well, as secondary efficacy endpoints. An aggregate score for the primary efficacy endpoint related to the selected five COVID-19 symptoms is deemed appropriate in view of the observed heterogeneity in COVID-19 symptom profiles. Not all subjects experience the same symptoms or degree of symptom severity. For example, some subjects experience trouble breathing but are free of dry or

hacking cough. Others have no difficulty breathing but report chest congestion or coughing. This situation supports an argument against focusing on one or two symptoms, as a significant number of subjects may not have experienced those symptoms. It also supports an argument to use an aggregate score, since consideration of a larger number of symptoms makes the endpoint applicable to a larger number of subjects. Based on analysis of blinded data obtained from the study, more than 92% of subjects who received at least one dose of study drug had an aggregate symptom score higher than 5 at baseline (Day 0). The main reason why a few subjects do not have an aggregate baseline score higher than 5 is that they get well rather quickly, even before starting study drug. Such subjects will be excluded from the FAS.

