8 TABLES, LISTINGS AND FIGURES

8.1 List of Tables

The Tables to be generated include, but not limited to the following:

CONDUCT OF STUDY

14.1.1	Disposition of Subjects: All Enrolled Subjects
14.1.1.1	Major Protocol Deviations: Full Analysis Population
14.1.2.1	Demographics and Baseline Characteristics: Intent-to-Treat Population
14.1.2.2	Demographics and Baseline Characteristics: Full Analysis Population
14.1.2.3	Demographics and Baseline Characteristics: Per Protocol Population
14.1.2.4	Demographics and Baseline Characteristics: Safety Population
14.1.3	Prior and Concomitant Medications by ATC Level 2 and Preferred Term: Safety
	Population

PRIMARY EFFICACY ENDPOINTS

[figure not shown]
14.2.1.1	Attainment of Serum 25D Levels >=50 ng/mL by Visit: Full Analysis Population
14.2.1.2	Attainment of Serum 25D Levels >=50 ng/mL by Visit: Per Protocol Population
14.2.1.3	Attainment of Serum 25D Levels >=50 ng/mL by Visit and by Subgroups: Full
	Analysis Population
14.2.1.4	Attainment of Serum 25D Levels >=50 ng/mL by Visit and by Subgroups: Per
	Protocol Population
14.2.1.5	Time to Resolution of COVID-19 Symptoms Based on FLU-PRO Plus COVID-
	19 Five Symptom Aggregate Score: Full Analysis Population
14.2.1.6	Time to Resolution of COVID-19 Symptoms Based on FLU-PRO Plus COVID-
	19 Five Symptom Aggregate Score: Per Protocol Population
14.2.1.7	Time to Resolution of COVID-19 Symptoms Based on FLU-PRO Plus COVID-
	19 Five Symptom Aggregate Score - Cox Proportional Hazards Model Summary
	of Effects: Full Analysis Population
14.2.1.8	Time to Resolution of COVID-19 Symptoms Based on FLU-PRO Plus COVID-
	19 Five Symptom Aggregate Score - Cox Proportional Hazards Model Summary
	of Effects: Per Protocol Population
14.2.1.9	Tipping Point Analysis for Time to Resolution of COVID-19 Symptoms Based
	on FLU-PRO Plus COVID-19 Five Symptom Aggregate Score: Full Analysis
	Population
14.2.1.10	Tipping Point Analysis for Time to Resolution of COVID-19 Symptoms Based
	on FLU-PRO Plus COVID-19 Five Symptom Aggregate Score: Per Protocol
	Population
14.2.1.11	Time to Resolution of COVID-19 Symptoms Based on FLU-PRO Plus COVID-
	19 Five Symptom Aggregate Score by Subgroups: Full Analysis Population
14.2.1.12	Time to Resolution of COVID-19 Symptoms Based on FLU-PRO Plus COVID-
	19 Five Symptom Aggregate Score by Subgroups: Per Protocol Population

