- 14.2.2.3 Summary of Secondary Efficacy Endpoints Related to Resolution of FLU-PRO Plus Symptoms on or Before Day 10: Full Analysis Population
- 14.2.2.4 Summary of Secondary Efficacy Endpoints Related to Resolution of FLU-PRO Plus Symptoms on or Before Day 10: Per Protocol Population

14.2.2.5 Summary of Other Secondary Efficacy Endpoints: Full Analysis Population 14.2.2.6 Summary of Other Secondary Efficacy Endpoints: Per Protocol Population Supplemental Analysis of Time to Resolution of Individual FLU PRO Plus 14.2.2.7 Symptoms: Full Analysis Population Supplemental Analysis of Time to Resolution of Individual FLU PRO Plus 14.2.2.8 Symptoms: Per Protocol Population 14.2.2.9 Severity of COVID-19 Illness as Evidenced by Quality of Life Measures Using the FLU-PRO Plus Questionnaire at Each Visit: Full Analysis Population Severity of COVID-19 Illness as Evidenced by Quality of Life Measures Using 14 2 2 10 the FLU-PRO Plus Questionnaire at Each Visit: Per Protocol Population Duration of COVID-19 Illness as Evidenced by Quality of Life Measures Using 14.2.2.11 the FLU-PRO Plus Questionnaire: Full Analysis Population: Full Analysis Population 14.2.2.12 Duration of COVID-19 Illness as Evidenced by Quality of Life Measures Using the FLU-PRO Plus Questionnaire: Per Protocol Population 14.2.2.13 Clinical Course of COVID-19 as a Function of Serum 25D Concentration 50 ng/mL by Visit: Full Analysis Population Clinical Course of COVID-19 as a Function of Serum 25D Concentration 30 14.2.2.13.1 ng/mL by Visit: Full Analysis Se Clinical Course of COVID-19 as a Function of Serum 25D Concentration 100 14.2.2.13.2 ng/mL by Visit: Full Analysis Population 14.2.2.14 Clinical Course of COVID-19 as a Function of Serum 25D Concentration 50 ng/mL by Visit: Per Protocol Population 14.2.2.14.1 Clinical Course of COVID-19 as a Function of Serum 25D Concentration 30 ng/mL by Visit: Per Protocol Population Clinical Course of COVID-19 as a Function of Serum 25D Concentration 100 14.2.2.14.2 ng/mL by Visit: Per Protocol Population

SAFETY OUTPUTS

14.3.1.1	Overall Summary of Subjects with Treatment-Emergent Adverse Events: Safety Population
14.3.1.2	Incidence of Treatment-Emergent Adverse Events by SOC and Preferred Term: Safety Population
14.3.1.3	Incidence of Serious Treatment-Emergent Adverse Events by SOC and Preferred Term: Safety Population

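### The full analysis set's baseline symptom-score filter, needed only for symptom resolution, also limits the listed comparison of ER visits, low oxygen saturation, hospitalisation, ventilation and death, and no ITT or all-dosed efficacy table is listed

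*SAP*

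**What the plan says.** SAP 4.1 defines the widest set: "The intent-to-treat (ITT) population will include all randomized subjects". Protocol 9.5 then says that the FAS "is a subset of the ITT set from which subjects are excluded who did not receive any study drug", and also removes subjects whose baseline aggregate is 5 or less. SAP 4.3 words the same rule as subjects "excluded who did not receive any study drug or have a baseline aggregate five symptom score of >5". SAP 5.2 explains the restriction. In blinded study data, "more than 92% of subjects who received at least one dose of study drug had an aggregate symptom score higher than 5" at baseline. The few others had mostly recovered before starting drug, and "Such subjects will be excluded from the FAS".

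SAP 8.1 lists the first primary endpoint as "Attainment of Serum 25D Levels >=50 ng/mL by Visit: Full Analysis Population" (table 14.2.1.1) and the remaining secondary endpoints as "Summary of Other Secondary Efficacy Endpoints: Full Analysis Population" (table 14.2.2.5). Each has a per-protocol counterpart. The only table listed for the ITT population is demographics (14.1.2.1). SAP 6.10.1 and 6.10.2 name no analysis population. SAP 4.3 adds further exclusions for individual symptoms and quality of life, but lifts the filter for no endpoint. SAP 5.3 defines endpoints 3-7 as incidences over the whole 42-day study.

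**The concern.** The filter fits time to resolution. It has no such role for ER visits, low oxygen saturation, hospitalisation, ventilation or death, which can be observed in any randomised subject whatever the Day 0 score. A dosed subject who scores 5 on Day 0 and is later admitted or dies would be missing from the FAS incidence table and from its Chi-square or logistic comparison.

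A score of 5 or less does not guarantee that a subject is well. Secondary endpoint 1 adds the condition that no single symptom exceeds 1, so the SAP itself allows that a low aggregate can contain one worse symptom.

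The filter can also act after randomisation. Protocol 7.1.2 lets first dosing follow randomisation when drug is shipped, and SAP 6.1 prefers the baseline from the day before first dose. A subject who met the entry criteria and was randomised can therefore leave the FAS on a later score.

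These events are likely to be few in mild to moderate disease, so each one matters to the comparison.

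**Working it through.** **The plan's own figure.** Of the endpoints discussed here, only 25D attainment has a stated sample size (SAP 3.3: 25% vs 75%, one-sided alpha 0.025, 90% power, 19 per group). With pooled variance and no continuity correction:

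n = [1.960 × √(2 × 0.5 × 0.5) + 1.282 × √(0.25 × 0.75 + 0.75 × 0.25)]² / 0.50² = (1.386 + 0.785)² / 0.25 ≈ 18.9, so 19 per group, with 90.2% power. The stated figure is reproduced.

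**Does the filter threaten that test?** Removing 8% leaves 0.92 × 80 = 73.6 per arm. Power exceeds 99.99% at both 73.6 and 80 per arm, so it does not.

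**How many subjects are lost?** SAP 5.2 gives more than 92% above 5, so fewer than 1 − 0.92 = 8% fail. With all 160 dosed, that is fewer than 0.08 × 160 = 12.8, so at most 12, leaving at least 148 in the FAS (148/160 = 92.5%; 147/160 = 91.9% would contradict the SAP). Undosed randomised subjects are lost as well; the documents do not give their number.

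**Chance that an event is lost.** The documents give no event rates for endpoints 3-7, so a range is assumed. With 12 subjects excluded, P(at least one event among them) = 1 − (1 − r)¹²:

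| Assumed rate r | Probability |
|---|---|
| 1% | 11% |
| 2% | 22% |
| 5% | 46% |
| 10% | 72% |

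Subjects already nearly well may have lower rates than the study as a whole, so the upper rows may overstate their risk.

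**Effect of one lost event (assumed counts).** Uncorrected Chi-square:
- 4/80 vs 0/80: χ² = 160 × (4 × 80)² / (4 × 156 × 80 × 80) = 4.10, two-sided p = 0.043.
- After losing one event and 6 subjects per arm, 3/74 vs 0/74: χ² = 148 × (3 × 74)² / (3 × 145 × 74 × 74) = 3.06, p = 0.080.

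**Power for incidence endpoints (assumed rates, one-sided 0.025).**

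| Rates | 80 per arm | 73.6 per arm |
|---|---|---|
| 10% vs 2% | 57% | 53% |
| 15% vs 5% | 56% | 53% |
| 5% vs 1% | 32% | 29% |

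The average loss of power is small. The practical issue is the individual events.

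**The case against.** The case for leaving the plan alone has several parts.

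- **One population for the estimand.** SAP 2.2 targets patients with unresolved symptoms and puts 25D attainment and symptom resolution under that one population. This is a fair defence of the FAS for the two hierarchical tests. It does not extend to endpoints 3-7, which are outside the estimand statement.
- **Open table list.** SAP 8.1 says that its list is not exhaustive. A reader might infer that no ITT efficacy analysis is intended at all; the documents support only that none is listed. That table 14.2.2.5 holds endpoints 3-7 is likewise read from its title, although no other listed efficacy table covers them.
- **Per-protocol tables.** A reader might infer that these apply the filter too. SAP 4.4 defines the per-protocol set only by the absence of a major deviation before resolution and does not make it a subset of the FAS. The exclusion is shown for the FAS tables only.
- **Bias.** A reader might infer a distorted treatment comparison. The filter value is pre-dose and blinded, and the documents show no mechanism for a difference between arms.
- **Lost safety information.** A reader might infer that deaths go unreported. Serious treatment-emergent events are tabulated for the Safety Population (SAP 8.1), and all deaths are listed (SAP 6.9.1). Differing efficacy and safety counts would follow from differently labelled populations.
- **Nominal testing.** Endpoints 3-7 carry only nominal p-values, and deaths fall back to rates if too few. No confirmatory decision turns on them.
- **Direction of the filter.** Read literally, SAP 4.3 could be taken to exclude subjects above 5, and SAP 1 gives the SAP precedence over the protocol. SAP 5.2 and Protocol 9.5 settle the intent: subjects at or below 5 are excluded.

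These points limit the size and certainty of the concern. None gives a reason to apply a symptom-score filter to endpoints 3-7.

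**Conclusion.** The point holds as a cheap improvement. The listed FAS comparison of endpoints 3-7 omits fewer than 8% of dosed subjects, plus any undosed randomised subjects, although all of them can contribute events. The consequence is incomplete coverage and possible loss of rare events. For 25D attainment, an all-randomised version would add consistency but would not be expected to change the result under the design assumptions.

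This rests on three assumptions: that table 14.2.2.5 contains endpoints 3-7; that the share above 5 seen in blinded data also holds at the end of the study, with all 160 dosed, for the count of at most 12; and that event rates lie in the range shown, since the documents give none.

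**What to change.** 1. Limit the baseline score filter to the symptom-resolution endpoints.
2. State in SAP 6.10.2, and list in SAP 8.1, that endpoints 3-7 are analysed in all randomised subjects, or at least in all dosed subjects, with the FAS version as supportive.
3. For consistency, add an ITT version of 25D attainment.
4. Reword SAP 4.3 so that each exclusion stands alone: subjects who received no study drug, and subjects whose baseline aggregate score is 5 or below. This matches Protocol 9.5 and SAP 5.2 and removes the ambiguous negation.

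The cost is SAP wording and a few extra tables, with no new data. Event rates may be slightly diluted by subjects who were nearly well on Day 0, which the supportive FAS version would show.

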14.5 Treatment Compliance and Extent of Exposure: Full Analysis Population

8.2 List of Listings

To be added to support Table presentations

